1.2.1. Method of Assignment to Treatment

Patients who meet all criteria for enrollment will be randomized to treatment at the baseline visit. Assignment to treatment groups will be determined by a computer-generated random sequence using an interactive web-response system (IWRS), and then the site will be responsible for administering the treatment to the patients.

During Induction Period in Stage 1, approximately 100 participants will be randomized to 1 of 3 treatment groups in a 2:2:1 ratio:

- **CCI** μg LY3471851 Q2W SC,
- **CCI** μg LY3471851 Q2W SC, or
- placebo.

During Induction Period in Stage 2, up to approximately 100 additional participants will be randomized. The number of treatment groups and randomization ratio for Stage 2 will be determined and documented based on the last interim analysis of Stage 1. This decision making will occur following Stage 1, and the choice in allocation ratio including placebo may be adjusted to achieve the planned allocation across treatment arms.

The randomization will be stratified based on the following factors:

- previous advanced therapy failure status (yes/no)
- baseline corticosteroid use (yes/no), and
- baseline disease activity (MMS: [4 to 6] or [7 to 9]).

After the Induction Period, participants enter either Maintenance Period or Extension Induction and Extension Maintenance Periods, based on samples and assessments collected at Week 12, as described in Section 1.2.

2. Statistical Hypotheses

The primary objective is to demonstrate that LY3471851 is superior to placebo in achieving clinical remission at Week 12. Thus, the null hypothesis to be tested in relation to the primary estimand is that LY3471851 is not different from placebo with respect to the achievement of clinical remission at Week 12.

2.1. Multiplicity Adjustment

Multiplicity adjustment will not be employed in the analysis for this study.

3. Analysis Sets

Table KFAH.2 describes the populations planned for use in the analyses. The mITT population, as defined below, will be used in analyses of efficacy and PRO, unless otherwise noted in the SAP.

Table KFAH.2. Analysis Populations

Population	Description
ITT Population	All randomized participants. Participants will be analyzed according to the treatment to which they were assigned.
mITT Population	All randomized participants who receive at least 1 dose of study treatment (regardless of whether the participant fails to receive the correct treatment, or otherwise fails to follow the protocol). Participants will be analyzed according to the treatment to which they were assigned.
Safety Population	Same as mITT population
Pharmacokinetic Evaluable	All participants who receive at least 1 dose of investigational product and have sufficient blood sampling to allow for pharmacokinetic evaluation.

Abbreviations: GCP = Good Clinical Practice; ITT = intent-to-treat; mITT = modified intent-to-treat; SAP = statistical analysis plan.

Analyses of the maintenance dosing period and the extension periods will be based on the corresponding enrolled population as described in the table above.

4. Statistical Analyses

4.1. General Considerations

This SAP is intended to describe the analyses of all objectives, as well as safety assessments, for study KFAH.

Statistical analysis of this study will be the responsibility of Eli Lilly and Company (hereafter Lilly) or its designee. For primary and key secondary objectives, statistical analyses will be performed using SAS® Enterprise 7.1 or higher, SAS® Version 9.4 or higher, or RStudio Server Pro Version R.3.6.3. or higher.

Efficacy analyses will be conducted on the mITT population. Safety analyses will be conducted on the Safety population (same as mITT population, as described in Section 3). The efficacy analysis of the primary endpoint and secondary endpoints will be repeated for ITT population. Additional safety analyses may be performed as deemed appropriate.

The baseline modified Mayo Score (MMS) is calculated from valid daily diary entries obtained prior to endoscopy during the screening period and the endoscopic appearance of the mucosa at this screening endoscopy. For other efficacy, health outcome and safety assessments, baseline is defined as the last non-missing assessment recorded on or prior to the date of the randomization visit (Visit 2).

Any change to the data analysis methods described in the protocol will require an amendment ONLY if it changes a principal feature of the protocol. Any other change to the data analysis methods described in the protocol and the justification for making the change will be described in the clinical study report. Additional exploratory analyses of the data will be conducted as deemed appropriate.

Not all displays and analyses described in this SAP will necessarily be included in the CSR. Not all displays will necessarily be created as a “static” display. Some displays may be incorporated as interactive display tools instead of or in addition to a static display. Any display described in this SAP and not provided in CSR would be available upon request.

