The sponsor intends for the transition from Stage 1 to Stage 2 to be seamless, with participant screening and enrollment activities occurring continuously in the transition period. The study IWRS will allocate newly enrolling participants to groups according to the Stage 1 randomization ratio until the Stage 2 groups have been decided upon and implemented. The randomization ratios are described in Section 9.2.

Study Periods

This study has multiple periods, as shown the schema in Section 1.2.

Screening period

This period begins with Visit 1, which occurs 5 weeks (or less) before the planned randomization visit. A participant's screening evaluations must be completed and reviewed to confirm the participant's eligibility before randomization and dosing occurs at Visit 2.

Blinded induction and blinded maintenance periods

The double-blind, placebo-controlled, 12-week induction treatment period begins at Visit 2. Dosing, sample collection, and assessments continue Q2W, as shown in the SOA. Between Week 12 and Week 14, based on samples and assessments collected at Week 12, participants will be classified as either "Week 12 Responders" or "Week 12 Nonresponders" based on the "clinical response" criteria defined in Section 8.1.

- "Week 12 Responders" will continue to receive their same randomly assigned treatment throughout the blinded 40-week Maintenance Period, with the final dose occurring at Week 50 and the last maintenance assessments and sample collections at Week 52.
- "Week 12 Nonresponders" will enter the Extension Induction and Extension Maintenance Periods.

Extension induction and maintenance periods

Beginning at Week 14, participants who were classified as Week 12 Nonresponders will receive the high dose (CC1 μ g) of LY3471851 Q2W, unless a lower dose is selected for Stage 2 based on interim analyses.

Between Week 26 and Week 28, based on samples and assessments collected at Week 26, these participants will again be classified according to their response status (responder or nonresponder).

- Participants who are classified as responders based on the samples and assessments at Week 26 will continue to receive LY3471851 Q2W as maintenance through the remainder of the study. These participants have their final dose at Week 50 and their last maintenance assessments and sample collections at Week 52.

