6.1. Study Interventions Administered

Study interventions

In Stage 1, this study involves 2 dose levels of LY3471851, as well as placebo. Depending on the interim analyses and seamless adaptation described in Section 4.1, the study may involve these and/or other dose levels of LY3471851, as well as placebo, in Stage 2.

Treatment Name:	LY3471851	Placebo
Dosage Formulation:	0.6-mL vial delivers 0.9 mg LY3471851	0.9% sodium chloride
Dosage Levels:	CC1 µg CC1 µg new doses ^a	not applicable
Routes of Administration:	subcutaneous injection	subcutaneous injection
Dosing Instructions:	dosing Q2W	dosing Q2W

^a New doses added in Stage 2 may be lower than CC1 µg or greater but will not exceed CC1 µg.

LY3471851 drug product will be provided as a sterile solution in a single-use vial for SC injection. The drug product vials will be supplied in cartons with the appropriate quantity specific to the planned dispensing schedule. An unblinded pharmacist or other unblinded qualified individual will prepare the study intervention for SC dosing (see Section 6.3). When prepared for dosing according to the detailed instructions provided by the sponsor, it will not be possible to distinguish LY3471851 from placebo.

Monitoring after dose administration

All participants should be monitored for 30 minutes or longer after dosing, according to investigator practice or local standard of care.

Packaging and labeling

LY3471851 will be supplied by the sponsor or its designee in accordance with current Good Manufacturing Practice. Clinical trial materials will be labeled according to the country's regulatory requirements. All IPs will be stored, inventoried, reconciled, and destroyed according to applicable regulations.

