7.3. Lost to Follow up

A participant will be considered lost to follow-up if he or she repeatedly fails to return for scheduled visits and is unable to be contacted by the study site. Site personnel or designee are expected to make diligent attempts to contact participants who fail to return for a scheduled visit or were otherwise unable to be followed up by the site.

8. Study Assessments and Procedures

Study procedures and their timing are summarized in the SoA. Adherence to the study design requirements, including those specified in the SoA, is essential and required for study conduct.

All blinded assessments and sample collections should be completed before a dose is administered at the dosing visits.

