8.2.1. Vital Signs

Vital signs (blood pressure, body temperature, and pulse rate) will be measured when specified in the SoA and as clinically indicated. Additional vital signs may be measured during study visits if warranted, as determined by the investigator.

Blood pressure and pulse rate should be measured after the participant has been sitting for at least 5 minutes.

Unscheduled orthostatic vital signs should be assessed, if possible, during any AE of dizziness or posture-induced symptoms. If the participant feels unable to stand, sitting or supine vital signs will be recorded.

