9.4.4. Safety Analyses

Safety analyses will include AEs, SAEs, AESIs, C-SSRS, QIDS-SR16, vital signs, ECGs, and laboratory analytes, using the Safety Population data descriptively summarized by treatment group. Categorical safety measures will be summarized with incidence rates. Continuous safety measures will be summarized as mean change by visit. Exposure to study intervention will be calculated for each participant and summarized by treatment group.

Adverse events will be coded according to MedDRA and summarized by system organ class, preferred term, severity, and relationship to the study intervention. A TEAE is defined as an event that first occurred or worsened in severity after baseline, with baseline defined as all pre-existing conditions recorded at Visit 1 and any AEs recorded before the first dose of study intervention (that is, during the interval between Visits 1 and 2, and recorded with the time of onset before the first dose of study intervention). The treatment period will be used as the postbaseline period for the analysis. For events that are gender specific, the denominator and computation of the percentage will include only participants from the given gender.

The number and percentage of participants who experienced TEAEs, TEAEs by maximum severity, deaths, SAEs, TEAEs related to study intervention, discontinuations from the treatment due to an AE, and AESIs will be summarized. Treatment-emergent adverse events (all, by

maximum severity), SAEs including deaths, and AEs that lead to treatment discontinuation will be summarized and analyzed by MedDRA SOC and preferred term.

Treatment-related TEAEs (TEAEs related to study intervention) are defined as events that are indicated by the investigator on the eCRF to be related to treatment.

Adverse events of special interest will be identified by a standardized MedDRA query (SMQ) or a Lilly-defined MedDRA preferred term listing.

Follow-up emergent AEs, SAEs including deaths, and AEs that lead to study discontinuation will be summarized. All AEs, including pre-existing conditions, will be listed by participant, visit, preferred term, treatment group, severity, and relationship to the treatment.

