- Box plots for observed values: Values at each visit (starting at randomization) and change from baseline to each visit and to last postbaseline measure will be displayed in box plots for patients who have a baseline and at least 1 postbaseline visit. For visits included in the treatment period, patients will be included only if the visit occurs on or before the date of treatment discontinuation/completion. Follow-up visit will be the first visit that occurred during the Follow-up period. Individual measurements outside of reference limits will also be displayed using distinct symbols overlaying the box plot. Original-scale data will be used for the display but for some analytes (e.g., immunoglobulins) a logarithmic scale will be used to aid in viewing the measures of central tendency and dispersion. Unplanned measurements will be excluded. Descriptive summary statistics will be included in a table below the box plot. These box plots will be

used to evaluate trends over time and to assess a potential impact of outliers on central tendency summaries. A p-value for change from baseline to endpoint will be provided using an ANCOVA model with explanatory term for treatment and the baseline value as a covariate. Endpoint will be the last observation where patient is on treatment.

- Treatment-emergent high/low analyses: The number and percentage of patients with treatment-emergent high and low laboratory results at any time will be summarized by treatment group. Planned and unplanned measurements will be included. A treatment-emergent **high** result is defined as a change from a value less than or equal to the high limit at all baseline visits to a value greater than the high limit at any time during the treatment period and up to 60 days after treatment discontinuation. A treatment-emergent **low** result is defined as a change from a value greater than or equal to the low limit at all baseline visits to a value less than the low limit at any time during the treatment period and up to 60 days after treatment discontinuation. The Fisher's exact test will be used for the treatment comparisons.

For laboratory analyte measurements collected qualitatively, a listing of abnormal findings will be created. The listing will include patient ID, treatment group, laboratory collection date, analyte name, and analyte finding.

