4.6.6. Vital Signs and Other Physical Characteristics

Vital signs and physical characteristics include systolic blood pressure (SBP), diastolic blood pressure (DBP), pulse, weight, BMI, and body temperature. Original-scale data will be analyzed. When these parameters are analyzed as continuous numerical variables, unplanned measurements will be excluded. When these parameters are analyzed as categorical outcomes, planned and unplanned measurements will be included.

Vital signs and physical characteristics will be summarized and analyzed for the following periods:

- Induction Period

- Maintenance Period
- Extension Period

The planned analyses described for the laboratory analytes in Section 4.6.5 will be used to analyze the vital signs and physical characteristics.

Table KFAH.5 defines the low and high baseline values as well as the criteria used to define treatment-emergence based on postbaseline values. Postbaseline values include all values after baseline in the treatment and follow-up periods. The blood pressure and pulse rate criteria are consistent with the document *Selected Reference Limits for Blood Pressure, Orthostasis, and ECG Numerical Parameters (Including Heart Rate) for Use in Phase II-IV Clinical Trials Version 1.1* approved on 8 March 2013 as recommended by the Lilly Cardiovascular Safety Advisory Committee (CVSAC).

Table KFAH.5. Categorical Criteria for Abnormal Treatment-Emergent Blood Pressure and Pulse Measurement, and Categorical Criteria for Weight Changes for Adults

	Low	High
Systolic Blood Pressure (mm Hg)	≤ 90 (low limit) and decrease from lowest value during baseline ≥ 20 if > 90 at each baseline visit	≥ 140 (high limit) and increase from highest value during baseline ≥ 20 if < 140 at each baseline visit
Diastolic Blood Pressure (mm Hg)	≤ 50 (low limit) and decrease from lowest value during baseline ≥ 10 if > 50 at each baseline visit	≥ 90 (high limit) and increase from highest value during baseline ≥ 10 if < 90 at each baseline visit
Pulse (beats per minute)	< 50 (low limit) and decrease from lowest value during baseline ≥ 15 if ≥ 50 at each baseline visit	> 100 (high limit) and increase from highest value during baseline ≥ 15 if ≤ 100 at each baseline visit
Weight (kilograms)	(Loss) decrease $\geq 7\%$ from lowest value during baseline	(Gain) increase $\geq 7\%$ from highest value during baseline

[figure not shown]
Abbreviation: mm Hg = millimeters of mercury.

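### The safety baseline is cut at the date of Visit 2 rather than at the first dose, so an unplanned abnormal value taken after the Day 1 injection can be classed as baseline in the categorical laboratory and vital-sign tables

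*SAP*

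**What the plan says.** SAP 4.1 gives one baseline rule for safety assessments: "baseline is defined as the last non-missing assessment recorded on or prior to the date of the randomization visit (Visit 2". Protocol 9.4.1 states the same rule, so neither document corrects the other. The cut is a calendar date, with no clock time and no reference to dosing.

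The first dose falls on that date. Protocol 4.1 requires review of "eligibility before randomization and dosing occurs at Visit 2".

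Planned values are protected by the opening of Protocol Section 8: "All blinded assessments and sample collections should be completed before a dose is administered at the dosing visits". Unplanned values are not. Protocol 8.2.1 lets the investigator take additional vital signs at a visit, and Protocol 8.2.5 and Appendix 2 (10.2.1) allow additional laboratory tests at any time.

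Two categorical analyses take unplanned values in:

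- Laboratory high/low results (SAP 4.6.5): "Planned and unplanned measurements will be included". A treatment-emergent result needs values within the limit at all baseline visits, then a value beyond it during treatment or within 60 days after discontinuation.
- Vital signs (SAP 4.6.6): "When these parameters are analyzed as categorical outcomes, planned and unplanned measurements will be included". Table KFAH.5 counts a low systolic pressure only if it is 90 mm Hg or less, at least 20 below the lowest baseline value, and pressure was above 90 at each baseline visit.

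Adverse events follow a different rule. Protocol 9.4.4 counts as baseline the pre-existing conditions and "any AEs recorded before the first dose of study intervention", and SAP 4.6.2.1 also ends the adverse-event baseline at the first dose.

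**The concern.** A safety baseline should describe the participant before exposure. Here it can include a measurement made after the first injection, and because the rule takes the last value of the day, that measurement replaces the true pre-dose one.

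Two things follow in the categorical tables. The Day 1 abnormality is not counted as treatment-emergent. The participant may also fail the requirement of normal values throughout baseline, so later abnormal values of that parameter in that direction are not counted either. If unplanned post-injection abnormalities are more frequent on active drug than on placebo, both effects shrink the difference between arms. Day 1 is the first exposure to study drug, so it is a day on which acute changes are of interest.

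**Working it through.** The plan gives no figure that depends on this rule, so there is nothing to reproduce. The check applies the rules literally to constructed records under two cuts: (A) all values dated on or before Visit 2 are baseline; (B) only values before the first dose are baseline.

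**Low systolic pressure, Table KFAH.5.** Constructed values in mm Hg: Visit 1, 120; Visit 2 pre-dose, 118; Visit 2 unplanned post-dose, 85; Week 2, 88.

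- Cut A: baseline values are 120, 118 and 85, and the last is 85. Since 85 is not above 90, the condition at each baseline visit fails. Abnormal values counted: 0.
- Cut B: baseline values are 120 and 118, all above 90, and the lowest is 118. Day 1: 85 ≤ 90 and 118 − 85 = 33 ≥ 20, counted. Week 2: 88 ≤ 90 and 118 − 88 = 30 ≥ 20, counted. Abnormal values counted: 2.

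**High laboratory value, SAP 4.6.5.** Assumed upper limit 40. Constructed values: 25 at Visit 1; 28 pre-dose and 55 post-dose at Visit 2; 60 at Week 2.

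- Cut A: 55 > 40 is a baseline value, so the condition at all baseline visits fails. Counted: 0.
- Cut B: baseline values 25 and 28 are within the limit, and 55 and 60 exceed it. Counted: 2.

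The tables count participants, so each constructed participant moves from not counted (A) to counted once (B).

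**Is cut A the only possible reading?** No. SAP 4.1 fixes a single baseline value. The treatment-emergent rules speak of baseline visits, or of the lowest or highest value during baseline, and neither term is defined. SAP 1.2 starts the induction treatment period at Visit 2, so a post-dose Day 1 value also falls in the treatment period. Cut A is what the one stated rule gives, but a programmer could defend either.

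**Size.** The documents give no frequency of same-day post-dose measurements, so any count is an assumption. Protocol 9.2 plans about 40 on placebo and 40, 60 or 80 on a dose. If 1 or 2 of 40 on a dose and none of 40 on placebo were affected, cut A would show 0% v 0% where cut B shows 2.5% or 5% v 0%. For 2 v 0 the two-sided Fisher p-value is 2 × C(40,2)/C(80,2) = 2 × 780/3160 = 0.49. The loss would be in the description of a signal, not in a significance test.

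**The case against.** The case for leaving the text alone has several sound parts.

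- **Other analyses cover first-dose reactions.** Treatment-emergent adverse events are cut at the first dose. Hypersensitivity and cytokine release are found by MedDRA queries (SAP 4.6.3.2). Clinically relevant laboratory changes are reported as adverse events (Protocol 8.2.5). This stands. A reader might infer that the safety analysis as a whole would miss first-dose effects and make the drug look safer; the documents do not support that.
- **Reaction samples.** A reader might infer that blood drawn during a hypersensitivity reaction would be lost. The legible tests in Protocol 10.2.2 (drug concentration, N-methylhistamine, complements, cytokine panel) are not in the SAP Appendix 10 list of analysed analytes. Only additional routine tests are at issue.
- **Vital signs after dosing are not mandatory.** Protocol 6.1 says "All participants should be monitored for 30 minutes or longer after dosing" but requires no readings. Protocol 8.2.1 also says "Unscheduled orthostatic vital signs should be assessed, if possible, during any AE of dizziness or posture-induced symptoms", yet Table KFAH.5 has no orthostatic criterion. The main route is the optional additional vital signs in Protocol 8.2.1.
- **Continuous summaries.** Vital-sign summaries and laboratory box plots exclude unplanned values. The hepatic threshold counts in SAP 4.6.5.1 do not require a normal baseline, so a Day 1 value there would not block later ones.
- **The text is ambiguous.** A reader might infer that every affected participant is certain to be lost from the counts. That is too strong, because a programmer could place the value in the treatment period.

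These points narrow the effect without removing it. Optional unplanned values are foreseen, the categorical tables include them, and no passage moves a post-dose Day 1 value out of baseline.

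**Conclusion.** The concern holds, within limits. On the literal rule, an unplanned abnormal vital sign or routine laboratory value taken after the Day 1 injection is baseline in the high/low laboratory analysis and in Table KFAH.5, and it could disqualify later abnormal values of the same parameter in the same direction. Because baseline visits is undefined and the treatment period starts the same day, the outcome depends on who writes the program.

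The reach is confined to these categorical tables. The number of participants is unknown and probably small, since the effect needs an unplanned, same-day, post-dose value that crosses a limit. Any understatement of a drug effect further assumes that such values are more common on active drug, for which the documents offer no data. The conclusion also assumes that planned Visit 2 values are taken before dosing as required. It is worth correcting before unblinding because the remedy is cheap and the adverse-event rule already uses the right anchor.

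**What to change.** In SAP 4.1, define baseline for safety laboratory and vital-sign values as the last non-missing value before the date and time of the first dose. In 4.6.5 and 4.6.6, define baseline visits, and values during baseline, as all values before that time. State that later Day 1 values are post-baseline. Where a measurement time is missing, treat planned Visit 2 values as pre-dose and unplanned ones as post-dose.

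The cost is a few sentences and a small programming change. Protocol 6.4 already has the date and time of each dose entered in the eCRF. Protocol 9.4.1 requires an amendment only when a principal feature changes, which this should not be; the change and its reason can be given in the SAP and the study report. The downside is that the default may misassign some Day 1 values that have no recorded time.
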